9.1	Electronic Case Report Forms/Data Collection	26
9.2	Data Quality Assurance	27
9.3	Data Entry and Storage	27
10	SAMPLE SIZE AND STATISTICAL METHODS	27
10.1	Sample Size Rationale	27
10.2	Statistical Analysis Plan	27
10.3	Interim Analysis	29
11	GENERAL STUDY MANAGEMENT	29
11.1	Relevant Standards	29
11.2	Ethical Review	29
11.3	Protocol Deviations	29
11.4	Premature Termination of the Study	30
11.5	Source Documentation	30
11.6	Monitoring	30
11.7	Audits	31
11.8	Records Retention	31
11.9	Confidentiality and Publication	31
12	REFERENCES	32
13	ABBREVIATIONS	33
APPENDIX 1	Template Enrolment Log (Sample)	34
APPENDIX 2	Template Kit-Box Accountability Form (Sample)	35
APPENDIX 3	Template Source Document Record (Sample)	36
APPENDIX 4	Grading Scales & Measurement Instructions	37

One-month Clinical Evaluation of Oté Sensation Multi-Purpose Solution Care System

OTES-3301

PERSONNEL AND FACILITIES

SPONSOR:	OTE North America, [name] [contact]
PROJECT CO-ORDINATOR:	[name] OTE North America, Email: [contact]
INVESTIGATORS:	UK and US contact lens practitioners (listed separately)
STUDY LOCATION:	Approximately 10 sites in the UK and US (3-5 UK and 5-6 US) - listed separately
CLINICAL RESEARCH ORGANISATION:	Visioncare Research Ltd [name] [contact] [contact]
MEDICAL MONITOR:	[name] MPhil PhD FCOptom DCLP FAAO Visioncare Research Ltd [contact]-hour [contact] Email: [contact]
BIOSTATISTICIAN:	[name] MSc Visioncare Research Ltd [contact] Email: [contact]
DATA MANAGER:	[name] Visioncare Research Ltd [contact] Email: [contact]

One-month Clinical Evaluation of Oté Sensation Multi-Purpose Solution Care System**OTES-3301****SYNOPSIS**

OBJECTIVES: To test whether the Oté Sensation multi-purpose solution is substantially equivalent to another multi-purpose solution (Bausch & Lomb BioTrue® multipurpose solution).

STUDY DESIGN: One-month, approximately 200-subject, double-masked (care product), bilateral, randomized, comparative study. Subjects will be randomly assigned to use either the test or control solution.

TEST PRODUCT: Oté Sensation multi-purpose solution care system and Oté storage case (Oté Pharma, Uden, Nederland)
Constituents: PHMB 0.00002%, Polyquaternium-2 0.0001%, Sodium hyaluronate
The user instructions will include a rub and rinse step.

CONTROL PRODUCT: Bausch & Lomb BioTrue multipurpose solution and B&L storage case.
A sterile, isotonic solution that contains hyaluronan, sulfobetaine, poloxamine, boric acid, sodium borate, edetate disodium and sodium chloride and preserved with a dual disinfection system: polyaminopropyl biguanide 0.00013% and polyquaternium 0.0001%.

This will be used with a rub and rinse step.

CONTACT LENSES: The following six lens types will be used to represent a cross-section of lenses in use: ACUVUE® 2, ACUVUE® VITA® (Johnson & Johnson Vision Care), Air OPTIX® (Alcon), Biofinity®, Clariti (CooperVision), PureVision® (Bausch & Lomb)

Approximately 33 subjects will be allocated to use each lens type: 22 using the test MPS product and 11 using the control product. Each site will use four lens types.

NO. OF SITES: Approx. 10 (3-5 UK and 5-6 US) sites. Each site will enroll approx. 20 subjects.

NO. OF SUBJECTS: Total approx. 200 subjects (400 eyes), approx. 20 subjects/site. The aim is for at least 180 subjects to complete the study; 30 in each lens group (20 using the test solution and 10 using the control solution).

	Test Group	Control Group	Total Subjects
Site 1 to 10	~14	~7	~20
Total	133	67	200

STUDY POPULATION:	Volunteer subjects will be currently adapted soft contact lens wearers (>1 month of lens wear), be at least 18 years of age with contact lens sphere power requirement in the range +4.00 to -8.00D and refractive astigmatism of less than or equal to 0.75D in each eye.
VARIABLES:	
Comfort (0-10)
 
Average wearing time (WT), comfortable WT (hrs.)
 
Visual acuity (Snellen/logMAR)
 
Slit lamp findings, including corneal edema, limbal and bulbar hyperemia, vascularization, palpebral hyperemia and roughness, corneal staining, conjunctival staining, etc. (0-4)
 
Lens surface wettability (0-4)
 
Lens surface deposits (0-4, no. of spots)
 
Adverse events

IN VITRO MEASUREMENTS:	Deposit analysis in dark field illumination using a modified version of the method of Lowther et al (ICLC 1991;18:219-26) on approx. 60 lenses.
VISITS/SCHEDULE:	
There will be four scheduled visits (visit 1a and 1b may be conducted on the same day):
 
Visit 1a: Baseline
 
Visit 1b: Lens issue
 
Visit 2: 1 week follow-up (7 days \pm3 days) – WT 1-3 hours
 
Visit 3: 1 month follow-up (30 days \pm4 days)

STUDY END POINTS	
a) Safety Endpoints: Non-inferiority of slit lamp findings: limbal hyperemia, bulbar hyperemia, and corneal staining.
 
b) Efficacy Endpoints: Non-inferiority of comfort, visual acuity, surface wettability, lens deposits.

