3.2 Randomization

Subjects will be randomly assigned to use either the test or control solution. Two codes will be used for the test product and one code for the control so there are equal numbers of bottles of each code ('A', 'B' or 'C'). Subjects will also be randomly assigned to a lens type.

A random number generator (Microsoft Excel) will be used to determine the randomization of solutions and lens types. Each eligible subject will randomly be assigned to one of the lens care products and lens types using a blocking method and stratified by site. All sites will use both the test and control solutions. Each site will only use four of the six study lens types.

The randomization will be performed in stages. Firstly, the sites will be randomly assigned to four of the six study lens types. Secondly, subjects will be randomly allocated, by site, to one of the four lens types in blocks of four subjects. Thirdly, subjects within each site and lens type will be randomly allocated to one of the three solution codes (2 x Test, 1 x Control) in blocks of three subjects.

Subject ID numbers will be assigned consecutively to maintain randomization.

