4.7 Subject Replacement

Subjects that are discontinued or drop out of the study will not be replaced.

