7 METHODS AND ASSESSMENTS

7.1 Subject Recruitment

Recruitment materials (adverts, letters, etc.) must be approved by the Research Ethics Committee (REC) or Investigational Review Board (IRB). VCR will provide an approved advertisement, letter and telephone script for recruitment purposes. Any changes to these must be submitted back to the REC/IRB via VCR.

The procedures listed below will be conducted on all subjects. Variables must be collected in the order they are listed on the eCRF.

To participate in this clinical study, the Investigator will explain the Statement of Informed Consent to the subject, ensure each subject understands the subject instructions and determine subject eligibility.

The Investigator is required to answer any questions the subject has concerning the study or the information contained in the Statement of Informed Consent and Patient Information Sheet.

A subject is considered enrolled when he or she signs the Statement of Informed Consent. Other study-related may not be activities undertaken prior to obtaining informed consent.

All subjects enrolled should be accounted for, even if they are not dispensed lenses or study product. A signed Statement of Informed Consent constitutes enrolment. After enrolment, a subject is considered active and should be accounted for at every visit until the completion of or discontinuation from the study.

Each site will be expected to enroll approximately 20 subjects, up to a maximum of 24 subjects.

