10 SAMPLE SIZE AND STATISTICAL METHODS

10.1 Sample Size Rationale

The sample size was selected to be in agreement with ISO 11980:2012. The sample size assumes a drop-out rate of <10% and was rounded up to allow for equal subject numbers and even enrolment at each site.

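### At the nominal 10 sites of 20 subjects, the aim of 30 completers per lens (20 test, 10 control) has no drop-out reserve: even at best balance, two of the six lens groups enrol only 30

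*Combined protocol and SAP*

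**What the plan says.** The synopsis (No. of Subjects) states "The aim is for at least 180 subjects to complete the study; 30 in each lens group", and divides each group as "20 using the test solution and 10 using the control solution". On sites it gives "Approx. 10 (3-5 UK and 5-6 US) sites" and "Each site will enroll approx. 20 subjects". Under Contact Lenses, and again in section 5.3, it puts about 33 subjects on each lens type (22 test, 11 control), with four of the six types used at any one site.

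Section 3.2 randomizes in three stages. For the first, "Firstly, the sites will be randomly assigned to four of the six study lens types". Subjects are then allocated to one of the site's four lenses in blocks of four, and within site and lens to solution 2:1 in blocks of three. No rule is given for how often each lens must appear across sites.

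Section 10.1 says "The sample size assumes a drop-out rate of <10" per cent. Section 4.7 says "Subjects that are discontinued or drop out of the study will not be replaced". Sections 4.1 and 7.1 cap each site at 24 subjects, and section 7.1 defines the count: "A subject is considered enrolled when he or she signs the Statement of Informed Consent".

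**The concern.** The plan states a size for each lens group, and the reader needs to know whether the design delivers it. Three features work against it. Four lenses per site do not spread evenly over six types at ten sites. Losses are not made good. The per-lens aim equals the enrolment of the smallest group, so any loss there misses it. The first stage, as written, also does not guarantee even the best available balance.

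At stake is the per-lens description. The six lenses are there to represent the range of lenses in use, for a solution intended for all soft lenses, and the numbers per lens are what the plan offers in support of that.

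**Working it through.** **Inputs.** Completer aim 180 in total, 30 per lens, 20/10 by solution (synopsis). About 10 sites of about 20, four of six lenses per site (synopsis, 3.2). Lens blocks of four and solution blocks of three (3.2). Drop-out below 10% (10.1). No replacement (4.7). Cap of 24 per site (4.1, 7.1).

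**1. The plan's own total.** 180/0.9 = 200. Split evenly, 200/6 = 33.3 per lens, and 33.3 × 0.9 = 30.0. Both reproduce, with nothing to spare at 10%. The rounded 33, 22 and 11 give 29.7, 19.8 and 9.9. That is only rounding, and I put no weight on it.

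**2. The site structure.** Lens blocks of four give 20/4 = 5 subjects per site and lens. Ten sites give 10 × 4 = 40 cells, and 40/6 = 6.67 sites per lens, which is not a whole number. The most even split is 7, 7, 7, 7, 6, 6 sites, that is 35, 35, 35, 35, 30, 30 enrolled. The example lens sets in section 5.3, rotated over ten sites, give this same split.

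**3. Expected completers at 10% drop-out.** 35 × 0.9 = 31.5 (21 test, 10.5 control) in four lenses. 30 × 0.9 = 27 (18 test, 9 control) in two.

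**4. Chance that all six lenses reach 30**, assuming independent losses at rate d: P(30 of 30)² × P(at least 30 of 35)⁴.

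| d | P(30 of 30) | P(≥30 of 35) | All six |
|---|---|---|---|
| 0% | 1 | 1 | 100% |
| 1% | 0.7397 | 1.0 | 55% |
| 2% | 0.5455 | 0.9999 | 30% |
| 5% | 0.2146 | 0.9927 | 4.5% |
| 10% | 0.0424 | 0.8684 | 0.1% |

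**5. The 20/10 split.** Five per cell does not divide by solution blocks of three. Each cell holds one full block (2 test, 1 control) plus two subjects from the next block, who are both test with probability 1/3 and otherwise one of each.
- A 30-subject lens has exactly 20/10 only if 2 of its 6 cells have the test-test remainder: 15 × (1/3)² × (2/3)⁴ = 240/729 = 0.329.
- A 35-subject lens has at least 20/10 if at most 4 of its 7 cells do: 1 − (84 + 14 + 1)/2187 = 0.955.
- All six with no drop-out at all: 0.329² × 0.955⁴ = 0.09. By simulation it is about 0.2% at 5% drop-out and about 0% at 10%.

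**6. If the first stage were an unconstrained draw** (each site takes any of the 15 sets of four, equally likely), simulation gives a smallest lens group averaging about 23 enrolled and about 20 completers at 10% drop-out.

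**7. Other figures the documents allow**, best balance, 10% drop-out:

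| Sites × subjects | Smallest lens enrolled | Expected completers | All six reach 30 |
|---|---|---|---|
| 9 × 20 | 30 | 27 | – |
| 10 × 20 | 30 | 27 | 0.1% |
| 11 × 20 | 35 | 31.5 | about 56% |
| 10 × 24 | 36 | 32.4 | 88% |

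At 10 × 24 and 5% drop-out the chance is 99.6%. Adding the 20/10 condition at 10 × 24 gives about 63% at 10% drop-out and about 95% at 5%.

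**The case against.** **A reader might infer that the aim cannot be met. The documents do not support that.** Site and subject numbers are approximate, the stated country ranges add to 8–11 sites, and the cap is 24. Ten full sites on a balanced plan would reach 30 in every lens with probability 88% at 10% drop-out. Ten per cent is also a ceiling, not an expectation. All of this stands. But filling every site means 10 × 24 = 240 enrolled, not the stated 200, and it works only with a balanced plan. Under an unconstrained draw the chance at 10 × 24 and 10% drop-out is only about 10%.

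**A reader might infer that the smallest group will usually be far below 30 enrolled.** That holds only under the unconstrained draw. Section 3.2 is silent on balance across sites, but it does describe blocking, and the examples in section 5.3 look like a rotation in which each lens is in two of three sets. A balanced plan may well be intended. The silence justifies asking for a statement. It does not establish imbalance.

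**A reader might infer that the total of 180 also fails, because enrolment is counted from consent.** An assumed 5% failure at screening or fitting would give 200 × 0.95 × 0.9 = 171 (180 to 162 for 0–10%). The documents give no such rate, and section 4.2 describes the 200 as users of the two solutions. Under section 7.4, lens and solution are assigned only after eligibility is confirmed, so screening failures use no lens place, although failures at the trial fit in section 7.5 would. The count is ambiguous, and this is a minor wording matter.

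**Impact.** No hypothesis in section 2.1 is per lens. The models in section 10.2 contain solution, visit, their interaction, site and subject, but not lens, and the additional analyses are not by lens. This stands in full. It limits the point to the stated per-lens figures.

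**Conclusion.** The concern holds as an inconsistency between a stated size and the nominal design. At 10 × 20 the best plan leaves two lens groups with exactly 30 enrolled and so no reserve. At the 10% ceiling they expect 27 completers each, three short of the aim. The chance that all six groups reach 30 is about 0.1% at 10% drop-out and 4.5% at 5%. The 20/10 split would hold in every lens only about 9% of the time even with no losses.

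These figures assume exactly ten sites of 20, best balance and independent losses. The smallest group of about 23 enrolled and 20 completers further assumes an unconstrained first stage, which is one reading of section 3.2. The overall 180 from 200 and the pooled non-inferiority tests are not in question.

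**What to change.** 1. In section 3.2, state that the first stage is a restricted draw in which each lens type is used at 6 or 7 of the 10 sites, and give the site-by-lens table.
2. In the synopsis, restate the per-lens figures as expected values: about 30–35 enrolled and about 27–31 completers per lens at 10% drop-out (about 18–21 test, 9–10 control). They should not read as a minimum of 30 (20/10). Nor should 27 become a new minimum: at 10 × 20, best balance and 10% drop-out, all six lenses reach 27 with probability only about 41%.
3. As a minor wording point, say whether the 200 counts consented or dispensed subjects, since sections 7.1 and 4.2 read differently.

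The cost is protocol wording and a constrained site list. The stated per-lens figure becomes slightly less favourable, and no analysis changes. If the sponsor wants 30 per lens as a true minimum, it needs more enrolment (the 10 × 24 row above) as well as the balance rule.

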1 INTRODUCTION

The contact lens (CL) care product Oté Sensation is a multi-purpose soft contact lens solution applicable to all soft contact lenses and is intended for cleaning, disinfection, rinsing and storage of lenses.

The product is CE-marked and has been marketed in Europe since January 2011. The product contains constituents already used in FDA-approved multipurpose solutions. The disinfecting agents are polyheximethylene biguanide (PHMB) and polyquaternium which are widely used in other multi-purpose solutions, including BioTrue® (Bausch & Lomb).

There has been extensive pre-clinical testing to demonstrate sufficient safety and efficacy of the test solution, and scientific justification for conducting this clinical study (see Investigator Brochure).

The purpose of this study is to evaluate the clinical performance of the contact lens care product Oté Sensation in a representative population of soft contact lens wearers. For comparison, the widely used soft lens multipurpose solution, BioTrue (Bausch & Lomb) will be used as a control. This control product has been tested in previous clinical trials.²⁻⁴

2 STUDY OBJECTIVES

To test whether the Oté Sensation multi-purpose solution is substantially equivalent to another multi-purpose solution (Bausch & Lomb BioTrue).

2.1 Primary Hypotheses

2.1.1 Efficacy Hypotheses

The Oté Sensation multi-purpose solution will be non-inferior to the Bausch & Lomb BioTrue solution in terms of:

Comfort (0-10), a non-inferior bound of 1.0 will be used.

Visual acuity (logMAR VA), a non-inferiority bound of 0.05 will be used

Wettability (0-4), a non-inferior bound of 0.5 will be used.

Deposits (*in situ* 0-4), a non-inferior bound of 0.5 will be used.

2.1.2 Safety Hypotheses

The Oté Sensation multi-purpose solution will be non-inferior to the Bausch & Lomb BioTrue solution in terms of:

Corneal staining – type (mean grade, 0-4), a non-inferior bound of 0.5 will be used.

Limbal hyperemia (grade, 0-4), a non-inferior bound of 0.5 will be used.

Bulbar hyperemia (grade, 0-4), a non-inferior bound of 0.5 will be used.

3 STUDY DESIGN & RATIONALE

This will be a 1-month, 200-subject, double-masked (care product), bilateral, randomized, comparative study. Subjects will be clinically evaluated at the initial baseline visit (Visit 1), then after 1 week and 1 month of lens wear having been randomly assigned to use one of six lens types and either the test or control solution.

The risks and benefits to the subjects taking part in this study are detailed in the Informed Consent Form.

3.1 Masking

To prevent bias, several steps will be taken to keep the investigators and subjects masked to the identity of the assigned solution:

- Subjects will be identified by subject numbers, which are unrelated to study solution assignments.
- Solution bottles will be over-labelled ('A', 'B' or 'C') and packaged in kit-boxes so that the identity of the study solution is not revealed. Therefore, investigators must only dispense solutions for the study that have been provided by the sponsor or clinical research organisation (CRO).
- If for any reason the investigator needs to be unmasked to the solution type that the study subject is using, they should follow the decoding procedures which will be present in the investigator study binder.

If required, for purposes of a subject's safe clinical management, the investigators will be able to learn the identity of the solution being used by contacting the study Clinical Research Associate (CRA).

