4.2 Number of Subjects

Approximately 200 subjects will be enrolled in the study. Of these, approximately 133 subjects will use the test solution (Oté Sensation) and 67 subjects will use the control solution (Bausch & Lomb BioTrue).

Each subject will be required to attend up to four scheduled study visits over a period of approximately 1 month.

Subjects will be currently adapted soft contact lens wearers and will be recruited from the sites' existing patient database or via REC/IRB approved recruitment material. The anticipated enrolment period for the study is approximately 5 weeks.

The study population has been chosen to represent the range of patients that may use this multipurpose solution type.

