7.5 Visit 1b: Lens Fitting and Dispensing

The subjects will undergo a trial fit with the randomly allocated study lens type. If the appropriate study lenses are not available, a dispensing visit will be scheduled for another day.

- i. Slit lamp – confirm continued eligibility if on a different day
- ii. Record the parameters of the lenses on the Dispensing eCRF (lens type / lot number, lens parameters, etc.).

The performance of the lenses should be assessed after 10-15 minutes settling time and the following variables will be assessed:

- iii. Subjective comfort (0-10)

- iv. Vision
 - Monocular HC DVA (with CL)
 - Spherical over-refraction (SOR)
 - Monocular HC DVA with SOR
 - Binocular distance VA with CLs (Snellen/logMAR to the nearest letter)
- v. Surface characteristics
 - Lens surface wetting (0-4) and reason if Grade 1 or less.
- vi. Lens fit
 - Centration (0-2)
 - Corneal coverage (Y/N)
 - Post-blink movement (0-4)
 - Tightness on push-up (0-4)
 - Overall fit acceptance (0-4) and reason if Grade 2 or less.

To be successfully dispensed, subjects must show >Grade 2 lens fit acceptance with the trial lens and must be correctable to 6/12 (20/40) (0.30 LogMAR) or better in each eye. Trial lenses must also show >Grade 1 wettability.

Modifications to optimize the lens power will be allowed.

If the lens fit is acceptable, the investigator will issue the care system (Kit-box containing solution, lens case and instructions) that the subject was randomized to, and complete the Kit-box Accountability Log. All kit-boxes must be accounted for, even if they are not dispensed.

- vii. The subject will be instructed to wear the lenses on a daily wear basis (at least 8 hours a day, 6 days per week) until the 1-week follow-up appointment, unless they experience a problem which warrants lens removal. In this case the subject should contact the investigator.
- viii. The investigator or a clinical assistant will review the Participant Information Guide with the subject, which describes the procedures for contact lens wear, lens care, handling, cleaning and disinfecting. Any subject, who does not follow instructions to a degree that, in the Sponsor or Investigator's opinion, jeopardizes the subject's wellbeing or the validity of the study, will be discontinued.
- ix. The investigator will complete the Source Document Record (Appendix 3).

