11.5 Source Documentation

The eCRFs will be considered the source document, unless otherwise documented. The sponsor's representatives (Visioncare Research) will be authorized to gain access to the source documentation for the purposes of monitoring and auditing the study (see sections 11.6 and 11.7).

The Source Document Record must be completed to comply with GCP guidelines. It is a permanent record within the patient's records/notes that documents the subject's involvement in a clinical research study.

Contents of the source document record:

- Study number
- Subject ID
- Confirmation that subject met eligibility criteria
- Confirmation that subject signed the informed consent
- Confirmation that subject received a signed and dated copy of informed consent
- Date enrolled
- Details of Solution (code) assigned
- Details of lenses worn on study
- General notes
- Adverse events
- Exit date
- Whether subject completed the study or discontinued
- Investigator's signature

The Source Document Record will be completed for each subject upon enrolment and then updated when required, e.g. when subject exits the study.

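### Three shared bottle letters mean that one decoded control kit gives an investigator the arm of every subject at the site, and no masking is specified for the arm-specific lens case

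*Combined protocol and SAP*

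**What the plan says.** **Letters.** Section 3.1 relies on over-labelling: "Solution bottles will be over-labelled ('A', 'B' or 'C') and packaged in kit-boxes so that the identity of the study solution is not revealed". Section 3.2 explains the letters: "Two codes will be used for the test product and one code for the control so there are equal numbers of bottles of each code". At the last randomization stage the letters are allocated within each site and lens type, "in blocks of three subjects". All sites use both solutions. No key specific to a site, kit or subject is described.

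**Decoding.** Section 3.1 gives two routes: a procedure kept in the site binder, and a request to the CRA when safe management of a subject requires it. It does not say how other subjects on the same letter stay masked afterwards.

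**Where the letter is held.** The Source Document Record at each site must contain "Details of Solution (code) assigned" (Section 11.5), and the Appendix 3 template has a field for it.

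**Lens cases.** The synopsis and Table 1 (Section 5.1) give the test arm an Oté case and the control arm a B&L case. Section 7.5 has the investigator "issue the care system (Kit-box containing solution, lens case and instructions) that the subject was randomized to". Sections 3.1 and 5.1 apply over-labelling to the bottles. Section 5.1 also says that kit-boxes reach the sites sealed, and that both parties are to be masked.

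**The concern.** A letter shared by a whole arm protects each subject only while nobody at the site learns what any letter means. The control arm has a single letter, and the protocol that investigators follow prints the split of two test letters to one control. Learning the control letter therefore identifies the other two by elimination. A legitimate code-break for one subject can end masking for everyone else whose letter that investigator holds.

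The lens case is a second possible route. It differs by arm, travels in the kit and is used daily by the subject, yet no step to disguise it is stated.

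The protocol has the investigator issue the kit and describes no separate unmasked dispenser. The endpoints are mostly judgements: comfort is rated by the subject, and wettability, deposits, corneal staining, limbal hyperemia and bulbar hyperemia are graded 0-4 at the slit lamp. Visual acuity, a letter count, is the least exposed.

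**Working it through.** **Inputs.** Three letters, two test and one control (Section 3.2). About 200 subjects, of whom "approximately 133 subjects will use the test solution (Oté Sensation) and 67 subjects will use the control solution" (Section 4.2). About 20 subjects per site, maximum 24 (Section 4.1). Seven primary hypotheses (Sections 2.1.1 and 2.1.2).

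**1. The plan's own arm sizes.** 200 × 2/3 = 133.3 and 200 × 1/3 = 66.7, which match 133 and 67. Per lens type, 33 × 2/3 = 22 and 33 × 1/3 = 11, as in Section 5.3. Each letter thus covers about 200/3 = 66.7 subjects in the trial, and 20/3 = 6.7 to 24/3 = 8 at one site.

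**2. What one decode reveals.** Before any decode no arm is certain, and guessing test for everyone is right for 2/3 = 66.7%.

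- *Control letter decoded.* The other two letters must both be test. Share certain = 1/3 + 1/3 + 1/3 = 100% of subjects whose letter is visible.
- *Test letter decoded.* That letter is certain, for 1/3 of subjects. One of the other two is test and one is control, at 50:50. Best-guess accuracy = 1/3 × 1 + 2/3 × 1/2 = 66.7%, no better overall than before. Any later decode of a second letter completes the key.

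If a decode is equally likely for any subject (an assumption), it falls on a control subject 1/3 of the time and a test subject 2/3 of the time.

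**3. Reach.**

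| Coding | Kit decoded | Arms certain at one site (20-24 subjects) | Arms certain in the trial (200) if the key is shared |
|---|---|---|---|
| Three letters | Control | 20-24 (all) | 200 |
| Three letters | Test | about 7-8 | about 67 |
| One code per kit | Either | 1 | 1 (1/200 = 0.5%) |

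Without sharing, one investigator's 20 to 24 subjects are 20/200 = 10% to 24/200 = 12% of the trial.

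**4. Lens case, item by item.**

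| Kit item | Differs by arm? | Masking step stated? |
|---|---|---|
| Bottle | Yes | Yes, over-label (Sections 3.1, 5.1) |
| Lens case | Yes, Oté or B&L (synopsis, Table 1) | None stated |
| Outer box | Not stated | Supplied sealed (Section 5.1) |

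**5. Endpoints exposed.** Comfort, wettability, deposits, corneal staining, limbal hyperemia and bulbar hyperemia: six of seven.

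**The case against.** **Reach.** A reader might infer that one decode unmasks all 200 subjects. The documents do not support that. One investigator holds the letters of about 20 to 24 subjects, and no exchange of letters between sites is described. Use of one key at every site is the plain reading of Section 3.2, but is not stated in words. This objection stands and sets the size of the point.

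**Lens case.** A reader might infer that the case openly reveals the arm. The documents name each case's supplier; they do not say that the cases are branded, look different or are left undisguised. Sealed boxes also limit what is seen before dispensing. This stands too, so the case is a gap in the stated masking and not proven unmasking. The seal does not close the gap, because the subject must open the box to use the case, and Section 8.3 has the investigator collect the case after a serious event.

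**Direction and size of bias.** A reader might infer that lost masking pulls the difference towards zero and so favours non-inferiority. A grader who expects the products to be alike could do that while fully masked. Bias from unmasking needs a known arm and a preference, and the documents point to neither product. A preference for the control, which Section 1 calls widely used, would make non-inferiority harder to show. Section 10.1 gives no SD, so any inflated error rate would rest on assumed SDs and an assumed bias common to the whole trial.

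**Blocks of three.** A reader might infer that the block size should change as well. The letter is openly recorded after assignment, so predicting it adds nothing to unmasking at assessment, and assignment follows the eligibility checklist (Section 7.4). With about 20/4 = 5 subjects per site and lens type, larger blocks would often stay incomplete and disturb the 22/11 split. That change is not part of this point.

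**Frequency.** The documents do not let one estimate how often decoding would occur, and the binder procedure is not among them.

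**Conclusion.** The point holds as a cheap improvement. As written, one decoded or recognised control kit gives an investigator the arm of all their subjects, about 20 to 24 (10% to 12% of the trial). A decoded test kit gives the arm of about one third. These figures assume that the letters mean the same for every subject at a site, and that the investigator has access to the source records kept there.

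The missing masking step for the lens case is a separate gap, whose consequence depends on how the cases look. Six of the seven hypotheses could be affected. The documents support a risk of bias, but no statement of its direction or magnitude.

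**What to change.** 1. In Sections 3.1 and 3.2, replace the A/B/C letters with the kit-box numbers already used in the Appendix 2 log. Make each number unique and free of arm information. The 2:1 allocation can stay, implemented through a kit list held away from the sites.
2. In Section 11.5 and the Appendix 3 template, record the kit-box number in place of the solution letter.
3. Provide a separate code-break for each subject, through the binder or the CRA, so that a decode reveals one subject only.
4. Over-label the lens case or supply cases of identical appearance in both arms, and say so in Sections 3.1 and 5.1.

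The cost is relabelling and a kit list before packing, with a short protocol edit. It needs no extra subjects or visits, and the analysis does not change.
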